## 5. ELIGIBILITY CRITERIA

### 5.1. INCLUSION CRITERIA

- patients aged of 18 to 65 years
- patients with episodic migraine (<15 days / month) with at least 4 attacks per month

- patients with migraines with or without aura with diagnostic criteria per International Headache Society
- patients with a migraine for more than one year
- diagnosis age < 50 years
- patients with an available internet connexion to access Music Care application
- patients with minimal knowledge in informatics
- patients who sign their inform consent

## **5.2. NON-INCLUSION CRITERIA**

- patients aged less than 18 years
- patients with chronic migraine
- patients with epilepsy
- patients with a deficiency on auditive function
- patients with a disease that could be fatal within the study period.

## **5.3. PATIENT RECRUITMENT**

The recruitment of the patients will be done at Chronic Pain Department of GHSR site of Saint-Louis during their standard ambulatory care.

[figure not shown]
Inclusion and exclusion criteria will be checked by the responsible of the study during the inclusion visit. This study will enrol around 20 patients during a short period of time.

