## **2.4. JUSTIFICATION OF METHODOLOGIC CHOICES**

This study has been designed as a before-after study without control group. Intervention being realized under current practice, it will not be possible to propose a randomised trial with one arm is treated with music therapy and another one not.

The month before inclusion will serve as reference. Effect of music therapy will be evaluated during 3 months after inclusion, using a period of same duration of the reference one and using the same tools.

During the 3 months, patients will be followed every month during a visit realised at Chronic Pain Department of GHSR in order to evaluate if the patient is compliant in completion of migraine diary, uses correctly Music Care and if he is compliant with his program. During the visit, migraine evaluation will be evaluated.

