### 7.1. PRIMARY ENDPOINT

**Reduction of migraine crisis frequency of at least 50% after 3 months of treatment.**

The studied variable will be the monthly frequency of migraine crisis. Data collection will be done using a migraine agenda (annex 1), starting the month before inclusion and music therapy initiation. This agenda

should then be completed usually during study period under music therapy. During each monthly visit, a control will be done by the intern of general medicine associated to the study.

The primary endpoint will be obtained using the difference between mean crisis frequency during the month before music therapy initiation and the one obtained during the 3rd month of treatment.

A reduction of at least 50% at month 3 will be considered as music therapy efficacy on episodic migraine prevention.

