## 7.5. SCREENING VISIT

Screening visit will be managed by the algologist responsible of the study. It will be done between 4 months and 1 month before inclusion visit.

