### 7.5.1. PATIENT INFORMATION

During screening visit and before any evaluation or data collection, the investigator will inform the patient of the study and propose him to participate. The following points will be described:

- Objectives and design of the study,
- Data collection and processing, access rights.

Migraine agenda (usually used by the team) will be provided to the patient in order to complete the 1-month observational period.

During this visit, inclusion and exclusion criteria will be verified. If the patient agrees to participate, oral consent will be provided.

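### The protocol checks eligibility at two different visits and never says which month decides the attack-frequency criterion; if it is the reference month, regression to the mean enters the uncontrolled primary comparison

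*Protocol*

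**What the plan says.** Section 5.3 of the protocol puts the check at Day 0: "Inclusion and exclusion criteria will be checked by the responsible of the study during the inclusion visit". Section 7.5.1, describing the screening visit, says: "During this visit, inclusion and exclusion criteria will be verified". On the timing of that visit, section 7.5 says: "It will be done between 4 months and 1 month before inclusion visit". The diary for the reference month is issued at the same screening visit: "Migraine agenda (usually used by the team) will be provided to the patient in order to complete the 1-month observational period". The screening check therefore precedes the reference month, and the Day 0 check follows it.

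The criterion in section 5.1 reads "patients with episodic migraine (<15 days / month) with at least 4 attacks per month". No month, record or averaging period is named. The lower limit counts attacks and the upper limit counts days.

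The follow-up table in section 7.4 has no eligibility row. Its diary item at Day 0 is a check that the diary was completed. Section 7.6, on the inclusion visit, lists consent, questionnaires and training, but no eligibility check.

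Section 2.4 fixes the baseline: "The month before inclusion will serve as reference". Sections 7.1 and 9.2, with SAP sections 3.1 and 5.2, compare that month with the third month of treatment by a Wilcoxon signed rank test. Section 7.1 adds the interpretation: "A reduction of at least 50% at month 3 will be considered as music therapy efficacy on episodic migraine prevention". Neither document mentions regression to the mean.

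**The concern.** Monthly attack counts vary by chance. If a patient enters only when the reference-month count reaches 4, patients with a chance low month are turned away and patients with a chance high month are kept. The baseline is then too high on average, and the count tends to fall by Month 3 whatever is done in between. A control group would show the same fall and cancel it. This trial has none, so the fall goes straight into the estimate and the Wilcoxon test. The section 7.5.1 route avoids this because the reference month comes after the decision. The two sections therefore differ in statistical consequence as well as in wording.

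**Working it through.** **The plan's own figure.** Section 9.1 gives mean 8, SD 4, a 50% reduction (a difference of 4), power 90%, alpha 5% and 20 patients. With n = (SDd × (1.960 + 1.282) / 4)² and SDd = 4 × √(2(1 − ρ)):
- ρ = 0: SDd = 5.66, n = (5.66 × 3.242 / 4)² = 21.0, so 22.
- ρ = 0.1: SDd = 5.37, n = (5.37 × 3.242 / 4)² = 18.9, so 19.

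The stated 20 is reproduced within 2 patients. Section 9.1 gives mean 8 and SD 4 for patients who already meet the criteria, so they describe the population after selection.

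**Assumptions the documents do not give.** Clinic (source) mean, month-to-month correlation ρ, how the day limit acts on the attack count, and a two-sided test (favourable share 2.5%). The upper limit is modelled as a count of 14 or fewer, although it is stated in days.

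**Hand formula.** With the same true rate in both months, expected change ≈ (1 − ρ) × (source mean − selected baseline mean).
- Source mean 6, ρ = 0.65, limits 4–14, selected baseline 7.24: 0.35 × (6.00 − 7.24) = −0.43 attacks, or −6%.
- Source mean 6, ρ = 0.30, lower limit only, selected baseline 7.76: 0.70 × (6.00 − 7.76) = −1.23 (simulated −1.19, or −15%).
- Source mean 8, ρ = 0.30, limits 4–14, selected baseline 8.06: 0.70 × (8.00 − 8.06) = −0.04 (simulated −0.02).

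If an earlier month qualifies the patient, the reference month and Month 3 have the same expected count and the change is zero.

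**Simulation with no treatment effect.** Gamma-distributed true rates; Poisson or overdispersed monthly counts; SD about 4 in the source population; 20 patients per sample; Wilcoxon at two-sided 5%. Ranges are over ρ from 0.30 to about 0.6.

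| Source mean | Qualifying month and limits | Selected baseline mean (SD) | Change | Favourable rejections |
|---|---|---|---|---|
| 8 | Reference, 4–14 | 8.0–8.1 (2.8) | −0.1 to −0.3% | 3% |
| 8 | Reference, ≥4 only | 8.7–8.9 (3.6–4.0) | −4 to −6% | 6–8% |
| 8 | Earlier month, 4–14 | 8.0–8.1 (3.7–3.9) | about 0% | 2–3% |
| 6 | Reference, 4–14 | 7.2–7.3 (2.7) | −6 to −11% | 10–15% |
| 6 | Reference, ≥4 only | 7.8–7.9 (3.5–3.7) | −8 to −15% | 13–20% |
| 6 | Both months, 4–14 | 7.4–7.5 (2.7) | −4 to −9% | 8–12% |
| 6 | Earlier month, 4–14 | 6.4–6.8 (3.8–4.0) | about 0% | 2% |

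At source mean 9 with limits 4–14 on the reference month, the sign reverses: a rise of 2–6% and favourable rejections of about 1–2%.

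**Matching the plan's baseline.** With both limits on the reference month and a selected mean near 8, the selected SD is only 2.7–3.0, short of the stated 4. With the lower limit alone and the source mean set so that the selected mean is 8, the SD is 3.1–4.2. Two settings come within about 0.1 of SD 4:
- Rates with coefficient of variation 0.7 and Poisson months: fall about 9%, favourable rejections about 14%.
- Coefficient of variation 0.5 and monthly variance twice the mean: fall about 17%, favourable rejections about 23%.

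The most variable setting (0.7, variance twice the mean) slightly overshoots the SD and gives a fall of 18% with rejections of 26–29%. The least variable gives 5% and 7%.

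**The case against.** The strongest reply is that the mechanism is inferred. No passage says the reference diary decides eligibility. The Day 0 diary item concerns completion, and section 7.6 describes the inclusion visit without an eligibility check. Section 5.3 also has an innocent reading: signed consent is itself an inclusion criterion and is collected at Day 0, so a final check there is needed anyway. This stands. A reader might infer that the trial does select on its baseline month; the documents support only that it could, because they leave the deciding month open.

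A second reply is that the two limits cancel. They do at a clinic mean of about 8 with both limits acting on the count, and above that the bias runs against music therapy. This stands as one end of the range. It does not dispose of the point, because that case gives a selected SD below the planned 4 and because the upper limit is in days.

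A reader might also infer that regression alone could meet the efficacy definition in section 7.1. It could not: the largest artificial mean fall above is 18%, against a threshold of 50%. Larger false-positive rates arise if a clinic mean of 5 is assumed with limits 4–14, but that gives a selected baseline of 6.3–7.2 with SD 2.1–2.8, which does not match the plan's 8 and 4.

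**Conclusion.** The point holds as a conditional one. Sections 5.3 and 7.5.1 conflict, and no passage names the month or record behind "with at least 4 attacks per month". If the reference month is used, the estimated change and the Wilcoxon test can be biased. The size runs from nil or slightly unfavourable (both limits acting, clinic mean 8–9) to a fall of about 9–17% with favourable rejections of about 14–23% (mainly the lower limit acting, selected baseline near mean 8, SD 4). These figures rest on assumed clinic means, month-to-month variation and action of the day limit. The harm is to the size of the estimate and the meaning of a significant p-value. A screening-based check removes this source of bias, but not the regression that follows when patients seek care in a bad period.

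**What to change.** In sections 5.3 and 7.5.1, state one rule:
- The frequency criterion is judged at the screening visit, on a named record covering a period before the reference month.
- The reference-month attack count is not used to include or exclude anyone.
- Day 0 confirms only the remaining criteria, such as consent.

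In protocol section 7.1 and SAP section 3.1, describe the result as the change observed under music therapy instead of as its efficacy, since regression from care-seeking remains without a control group.

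The cost is a few sentences in the protocol and one in the SAP, with no added visit, patient or data item. The downside is that some enrolled patients will fall outside the frequency limits in the reference month, with fewer than 4 attacks or with 15 or more days, so the baseline spread is wider. In the simulations at source mean 8 the selected SD rises from about 2.8 to 3.7–3.9, still within the planned 4. At clinic mean 6, over a wider set of variance assumptions, it goes from 2.4–2.9 to 3.0–5.0.

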## **6. NATURE OF ROUTINE CARE ASSESSED IN THE RESEARCH**

### **6.1. ACT(S) IN STUDY**

The Music Care app is a receptive music intervention self-directed by the patient at home, allowing the patient to freely adjust the length of and choose the preferred style between different sequences of instrumental music. All musical pieces were recorded in high-quality recording studios with professional musicians. After a formation on how to use the application, the patient will have the possibility to choose, according to his musical preferences, between different music therapy sequences based « U » technique. Music Care utilizes the “U” technique (Figure 1), designed to gradually relax the listener. In the current study, music sequences during patients’ sessions were based on the mount “U”, and instrumental musical works were selected for a varying numbers styles (classical, jazz, world music, etc.) and adapted to the patient's style via patient request. The “U” technique is implemented using a musical sequence of 20 minutes that was divided into 5 different musical pieces at 3 to 4 minutes each. Initially, the objective is to represent the patient's state of tension by stimulating musical rhythm (80-95 beats per minute (bpm). From there, the remaining 4 sub-pieces are presented in a blended fashion in an attempt for the patient to gradually fall into a relaxed state via a gradual reduction in musical tempo (40-80 bpm), orchestral size, frequencies, and volume (descending arm of the “U”). The music session then reaches a phase of maximum relaxation (downward phase of the “U”) before a phase that gradually returns to baseline dynamics (ascending arm of the “U”).

Figure 1: The “U” sequence

Headphones were required (provided at time of treatment), and patient were instructed to lay down (to promote muscle relaxation) with their eyes closed and lighting to a minimum. Participants answered questions related the frequency, duration, and other migraine related questions throughout the treatment. At the end of the 3-month of treatment, participants underwent the same assessment as at baseline.

The objective of 1 to 2 daily sessions will be suggested to the patients according to their availability. Migraine crisis frequently implies a phonophobia, so it will be recommended to realise the sessions outside migraine crisis. As patient will manage his sessions as he wants, this information will be given without contraindicating music therapy during crisis if patient wants to do it.

The training to *Music care* software for the doctors in charge of the study will be done by a music therapist from AM-ARC, with a validated diploma and experience in clinical research, under the framework of the institutional training plan of the CHU.

## 7. EVALUATION CRITERIA

Primary and secondary endpoints are defined according to the last recommendations related to the evaluation of prophylactic migraine treatment of ANAES October 2002: « *Treatment is considered as efficient if crisis frequency is reduced of at least 50 %. It is also important to consider the reduction of medication consumption, intensity and duration of crisis. Evaluation is done after 3 months.* ». The methodology is consistent with guidelines of International Headache Society for clinical research on migraine.

### 7.1. PRIMARY ENDPOINT

**Reduction of migraine crisis frequency of at least 50% after 3 months of treatment.**

The studied variable will be the monthly frequency of migraine crisis. Data collection will be done using a migraine agenda (annex 1), starting the month before inclusion and music therapy initiation. This agenda

should then be completed usually during study period under music therapy. During each monthly visit, a control will be done by the intern of general medicine associated to the study.

The primary endpoint will be obtained using the difference between mean crisis frequency during the month before music therapy initiation and the one obtained during the 3rd month of treatment.

A reduction of at least 50% at month 3 will be considered as music therapy efficacy on episodic migraine prevention.

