STANDARD CARE NATURE EVALUATED IN THIS RESEARCH	Sessions of music therapy self-directed by the patient at home, using Music Care software via an internet connexion.
EVALUATION CRITERIA	
Primary evaluation criterion Reduction of migraine frequency of 50% after 3 months.
 
Secondary evaluation criteria Reduction of migraine intensity and duration, as well as acute treatment administration. Reduction of the emotional and functional impact.

PLANNED SAMPLE SIZE	20 patients
PLANNED CENTERS	1 centre: Chronic Pain Department of CHU-GHSR site of Saint-Louis
DURATION OF THE RESEARCH	
 
- Duration of inclusion period: 1 month
 
- Duration of patient participation: 3 months
 
- Total duration of the study: 4 months
 

STATISTICAL ANALYSIS	
Analysis of the primary endpoint The mean number of migraine crises per month before and after music therapy will be compared using the Wilcoxon Paired Test.
 
Analysis of secondary endpoints Quantitative variables before and after music therapy will be analysed using Wilcoxon Paired Test. Qualitative variables will be analyzed using McNemar Chi test.

EXPECTED RESULTS	
To propose a new therapeutic and non-drug approach in episodic migraine prophylaxis.
 
To improve the relationship between medical team and patients.
 
To reduce the treatment consumption.

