## 2. SCIENTIFIC JUSTIFICATION

Migraine is a frequent pathology, it affects 20% of the French population and represents 1 milliard euros of direct cost. It is a research topic largely studied under non-drug approaches. The ANAES provided in its migraine recommendations in October 2002 to use relaxation, biofeedback and stress management cognitive and comportemental therapies in the care of migraine patients.

Music therapy is a recent discipline with a trend of development in hospital services and in specialised ambulatory care centres. Several controlled studies allowed to validate the utilisation of music therapy in chronic or sharp pain, as well as in anxio-depressive disease. In this domain, the work of [name], psychologist and music therapist, helped using Music Care software to elaborate a standardised computerised method allowing its use by caregivers and patients themselves.

Researches on music therapy effect on migraine patients are few.

A first German study in 1999 evaluated the effect of *Psychophonia* software on migraine, informatic tool which build a sound sequence from EEG of the patient. This cohort study on 55 adult migraine patients showed a decrease of at least 50% of migraine crises in 56% of patients treated for 12 months.

A second German study in 2008 evaluated the effect of active music therapy and the use of butterbur root extract (Petalodex) in the prevention of child migraine. This randomised, controlled study based on 58 patients distributed under 3 arms (music therapy/ butterbur/placebo) demonstrated superiority of music therapy arm against placebo after 8 weeks, and the superiority of the 2 treatments against placebo at 6 months.

The demonstrated effects of music therapy on chronic pain and anxio-depressive disease allow to assume a benefic effect of this technique in the migraine.

Scientific data of music therapy on migraine patients are positive and suppose its interest in this indication, as in chronic pain, but additional and more specific studies are needed to evaluate its indication on this specific pathology. A clinical study with 2 arms might be helpful.

The standardised and validated music therapy technique named as *Music care* seems to be a useful tool in standard cares and clinical research.

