## 9. STATISTICAL ASPECTS

### 9.1. SAMPLE SIZE CALCULATION

Primary endpoint is the reduction on migraine crisis frequency before and after music therapy.

In the population of patients corresponding to inclusion criteria, mean number of migraine crisis per month can be estimated to 8 (standard deviation = 4) before intervention.

A reduction clinically significant would be a reduction of at least 50% of mean monthly number of migraine crisis after 3 months of care.

Under these conditions, 20 patients are needed to have this difference of 50% with a statistical power of 90% and an alpha equal to 5%.

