#### Analysis of primary endpoint

Monthly mean number of migraine crisis before music therapy will be compared to the one obtained at Month 3 using Wilcoxon signed rank test for paired (dependent samples). The analysis will be performed in intent-to-treat.

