5. STATISTICAL METHODS

5.1. SAMPLE SIZE CALCULATION

Primary endpoint is the reduction on migraine crisis frequency before and after music therapy.

In the population of patients corresponding to inclusion criteria, mean number of migraine crisis per month can be estimated to 8 (standard deviation = 4) before intervention.

A reduction clinically significant would be a reduction of at least 50% of mean monthly number of migraine crisis after 3 months of care.

Under these conditions, 20 patients are needed to have this difference of 50% with a statistical power of 90% and an alpha equal to 5%.

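### The primary Wilcoxon test does not examine the 50% efficacy rule, and neither document covers a significant reduction below 50%

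*Protocol*

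**What the plan says.** **The rule.** Protocol 7.1 and SAP 3.1 title the primary endpoint as a fall in crisis frequency of 50% or more after three months, and 7.1 turns this into a criterion: "A reduction of at least 50% at month 3 will be considered as music therapy efficacy on episodic migraine prevention". The threshold comes from the national recommendation cited in protocol section 7 and SAP section 3.

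**The unit.** The rule sentence names none. The sentence before it in 7.1 works with means: "The primary endpoint will be obtained using the difference between mean crisis frequency during the month before music therapy initiation" is set against the third month of treatment. The sample-size sections do the same; SAP 5.1 has "A reduction clinically significant would be a reduction of at least 50% of mean monthly number of migraine crisis after 3 months of care".

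**The analysis.** The synopsis says "The mean number of migraine crises per month before and after music therapy will be compared using the Wilcoxon Paired Test". Protocol 9.2, repeated in SAP 5.2, says "Monthly mean number of migraine crisis before music therapy will be compared to the one obtained at Month 3 using Wilcoxon signed rank test". No reference value other than no change is given. Protocol 9.2 leaves detail to the SAP, but SAP 5.2 adds none on this point. Confidence intervals are planned for baseline characteristics only.

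**The power statement.** Protocol 9.1 and SAP 5.1 name the endpoint without a threshold ("Primary endpoint is the reduction on migraine crisis frequency before and after music therapy") and then state that "20 patients are needed to have this difference of 50% with a statistical power of 90% and an alpha equal to 5"%.

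**The concern.** The criterion and the test answer different questions. A small p-value from the signed-rank test says that frequency changed. It does not say that frequency halved. A report could therefore present a significant result as efficacy although the plan's own efficacy criterion was missed.

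The sample-size sections make this easier. They call the endpoint simply the reduction, and they attach 90% power to the 50% figure, as if a significant test and a met criterion were the same event. The one quantity that bears directly on the criterion, the percentage reduction with its uncertainty, is not among the planned outputs.

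**Working it through.** **Inputs from the documents** (protocol 9.1, SAP 5.1): n = 20, baseline mean 8, SD 4, target fall 50% (8 to 4, a difference of 4), alpha 5%, power 90%.

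**Assumed, because the documents do not give them:** month-3 SD of 4, or proportional to the month-3 mean; within-patient correlation ρ of 0 or 0.5; two-sided testing unless stated.

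**1. Reproducing the 20 patients.** With SD 4 in both months and ρ = 0, the variance of the change is 2 × 4², so n = 2 × (z_alpha + z_power)² × (4/4)².
- Two-sided: 2 × (1.960 + 1.282)² = 21.01, so 22.
- One-sided: 2 × (1.645 + 1.282)² = 17.13, so 18.
- A paired t calculation inflated for the Wilcoxon test (divided by 0.955) gives 20 one-sided at ρ = 0, and 19 two-sided at ρ = 0.25.

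The stated 20 is therefore reproduced to within rounding. It is reproduced only as power to detect a non-zero change when the true change is 4.

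**2. Smallest significant observed fall** (paired t as an approximation to the signed-rank test; t with 19 df = 2.093). Critical fall = 2.093 × SD of change / √20.
- Month-3 SD 4, ρ = 0: SD of change 5.66; fall 2.65; 2.65/8 = 33%.
- Month-3 SD 4, ρ = 0.5: SD of change 4.00; fall 1.87; 23%.
- SD proportional to the mean, ρ = 0: the equation solves at 29%.
- SD proportional to the mean, ρ = 0.5: it solves at 21%.

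All lie well below 50%.

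**3. How often the two criteria part** (simulated trials of 20 patients, signed-rank test at 5%, bivariate normal). Share significant with an observed mean fall below 50%:
- True fall 30%, SD 4: 37% (ρ = 0) and 68% (ρ = 0.5).
- True fall 40%, SD 4: about 42–43% (ρ = 0) and 76% (ρ = 0.5).
- True fall 40%, SD proportional to the mean: up to 91%. With the month-3 SD set at 2: up to 94%.
- True fall 40%, gamma-Poisson count model with baseline mean 8 and SD 4: 87%.

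The reverse case, at least 50% but not significant, occurred in 0.2% of trials or fewer.

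**4. Precision of an observed fall from 8 to 4.** Log ratio of means, SE = √[(CV₁² + CV₂² − 2ρ·CV₁·CV₂)/20], with CV₁ = 4/8 = 0.5.
- Widest (month-3 SD 4, CV₂ = 1, ρ = 0): SE = √(1.25/20) = 0.250; 2.093 × 0.250 = 0.523; ratio 0.5 × e^(±0.523) = 0.296 to 0.844; reduction 16–70%.
- Narrowest (month-3 SD 2, CV₂ = 0.5, ρ = 0.5): SE = √(0.25/20) = 0.112; 2.093 × 0.112 = 0.234; ratio 0.396 to 0.632; reduction 37–60%.

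Even an observed halving leaves wide room on either side of 50%.

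**The case against.** **50% may be only the planning effect.** The sample-size sections can be read that way, and naming the effect to be detected is normal shorthand in a power statement. That reading does not displace 7.1 and SAP 3.1, which expressly make 50% the efficacy criterion.

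**7.1 already answers the split case.** Read literally, a significant fall of, say, 35% misses the endpoint. This has force: a reader might infer that the sponsor is free to choose the conclusion afterwards, and the documents do not go that far. But neither document states the consequence, and the sample-size sections describe the endpoint without the threshold.

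**The unit.** A reader might infer that the plan leaves it wholly open whether 50% applies to each patient or to the group. It does not: 7.1, 9.1 and SAP 5.1 all speak of the mean. The per-patient use is in the background, where a cohort study of a different tool "showed a decrease of at least 50% of migraine crises in 56% of patients treated for 12 months"; that defines nothing here. What stands is that the rule sentence does not repeat the unit.

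**Only about half of trials would observe a 50% fall when the truth is 50%.** This is arithmetically right but is no defect of this trial. It holds for almost any estimate at any sample size.

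**The normal model is crude.** With mean 4 and SD 4, about 16% of month-3 values are negative, and that model supplies the 33% threshold and the 16–70% interval. The count model has no negative values and still gives 87% in step 3.

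**Conclusion.** The concern holds in this form: the 50% rule, worded on the mean, is not what the Wilcoxon test examines, and no passage covers a significant reduction below 50%. Under the stated assumptions, significance starts at an observed fall of about 21–33%. At a true fall of 40%, a significant result that misses 50% is common (roughly 42–94% of simulated trials). The conflict runs in this direction only; meeting 50% without significance is negligible.

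The month-3 SD, the correlation and the simulation models are assumptions. The direction of the finding does not depend on them, but the percentages do.

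A reader might also infer that the sample size is wrong. The documents do not support that: 20 is reproducible as power against no change. What needs correcting is the description of what that power covers. The unstated sidedness and SD of the change, and the use of migraine days in protocol 4.1 against crises in 7.1, are separate matters to settle on their own.

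**What to change.** 1. **SAP 5.2.** Add the percentage reduction in mean monthly frequency with a 95% CI, naming the interval method. As support, add the proportion of evaluable patients (as defined in SAP 4) with at least a 50% reduction, with an exact 95% CI; 10 of 20 would give 27–73%. Base any statement about the 50% criterion on these and not on the Wilcoxon p-value.
2. **Protocol 7.1 and SAP 3.1.** State that the 50% rule applies to the group mean, and that a significant reduction below 50% shows a change but does not meet the efficacy criterion.
3. **Protocol 9.1 and SAP 5.1.** Reword the 90% as power to detect a non-zero change if the true reduction is 50%.

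The cost is two output lines from diary data already collected, some text, and a less favourable claim about the 50% criterion. No more patients are needed.

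Two alternatives cost more. Demoting 50% to a benchmark changes the efficacy criterion and would be a substantial amendment under protocol 12.2, needing a favourable ethics committee (CPP) opinion first. Testing formally that the reduction exceeds 50% is weak at this size: with a true fall of 60%, power at n = 20 is about 11–46% under the same assumptions (one-sided 2.5% paired t test of half the baseline minus month 3).
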